8.4. Secondary Endpoints

The following secondary endpoints will be calculated.

8.4.1. Additional Definitions of Hypotension

For each of the following definitions of hypotension, the time weighted average (TWA) of MAP or the mean duration will be calculated for each arm and the difference between the two arms. A 95% confidence interval will be calculated using the t-distribution. These additional definitions of hypotension will be calculated for the FAS population.

 Edwards	Revision Date: May 7, 2024	Rev	For Use Only by Affiliates of Edwards Lifesciences	Page 17
	Title	A randomized trial of the Hypotension Prediction Index in the cardiac operating room and the intensive care unit		

- Time Weighted Average (TWA) of MAP < 65 mmHg in the OR Period (T1)
- TWA of MAP<65 mmHg in the CVICU Period (T2)
- TWA of MAP < 65 mmHg in the CVICU Period, pre extubation (T3)
- TWA of MAP < 65 mmHg in the CVICU Period, post extubation (T4)
- Mean duration in minutes of MAP < 65 mmHg in the time periods of T1, T2, T3 and T4
- Mean duration in minutes of MAP < 60 mmHg in the time periods of T1, T2, T3 and T4
- Mean duration in minutes of MAP < 55 mmHg in the time periods of T1, T2, T3 and T4
- Mean duration in minutes of MAP < 50 mmHg in the time periods of T1, T2, T3 and T4

8.4.2. Clinical Endpoints

The following clinical endpoints will be analyzed. The clinical endpoints will be analyzed on the mITT population.

- Acute kidney injury (AKI), as defined by the modified KDIGO criteria, overall and by stage 1, 2 and 3
- Neurocognitive deficit, as evaluated by the MMSE, CAM-ICU 7, and bCAM assessments. [bCAM will be used for delirium screening for patients who are deemed ready for transfer to the floor per ICU attending team's assessment, even if they are physically in the ICU]
- Periprocedural Myocardial injury, measured with high-sensitivity Troponin I and defined by a threshold of 70 times the upper reference limit or >1400 pg/ml

For each of the clinical endpoints, the rate in each arm and the difference in the rates for the arms will be presented.

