Subjects will be randomized into two arms, the HPI arm and the non-HPI arm. The randomization will be done automatically by the Electronic Data Capture (EDC) system. The subject will be blinded. Due to the nature of the interventions, the investigators and treating anesthesiologist, anesthesia nurse, intensivist and critical care nurse will not be masked to group allocation.

The HPI arm will utilize the HemoSphere Advanced Monitoring Platform with the Acumen™ HPI Software Feature. The treating cardiac anesthesiologist/anesthesia nurse in the operating room and the critical care

THIS DOCUMENT CONTAINS CONFIDENTIAL AND PROPRIETARY INFORMATION OF EDWARDS LIFESCIENCES, LLC. IT MAY NOT BE REPRODUCED OR DISCLOSED WITHOUT PRIOR WRITTEN PERMISSION FROM EDWARDS LIFESCIENCES, LLC.

Edwards Lifesciences, Edwards, the stylized E logo, HemoSphere, Acumen IQ, Swan Ganz and ForeSight Elite are trademarks of Edwards Lifesciences Corporation.

nurses/intensivists/advance practice providers in the ICU will be trained to understand Acumen™ HPI Software Feature and the advanced hemodynamic parameters provided. The treating anesthesiologist, anesthesia nurse, intensivist, and critical care nurse will be provided with guidance by means of a flowchart suggesting what to treat and what the cause of hypotension is (see Figure 3. HPI Arm Protocol). Timing of treatment and choice of treatment is then left to the discretion of the attending intensivist and critical care nurse.

In the non-HPI arm, clinicians will be using non-protocolized standard of care to treat subjects.

[figure not shown]

Figure 3. HPI Arm Protocol

Note: Clinicians should validate the appropriateness of protocol recommendations, and provide treatment based upon their clinical judgment.

Schema

Screening and consenting subjects will occur during the pre-anesthesia visit. Once the subject is consented, the subject will undergo a Mini-Mental State Examination (MMSE).

After the subject has consented and prior to surgery, the subject will be randomized into the HPI arm or the non-HPI arm (control group). The randomization assignment must not be revealed to the clinicians until surgery. If a clinician randomizes the subject, they must not be involved in the care of the subject in the OR. A clinical research coordinator or a designee who is delegated to consent and/or randomize the

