THIS DOCUMENT CONTAINS CONFIDENTIAL AND PROPRIETARY INFORMATION OF EDWARDS LIFESCIENCES, LLC. IT MAY NOT BE REPRODUCED OR DISCLOSED WITHOUT PRIOR WRITTEN PERMISSION FROM EDWARDS LIFESCIENCES, LLC.

Edwards Lifesciences, Edwards, the stylized E logo, HemoSphere, Acumen IQ, Swan Ganz and ForeSight Elite are trademarks of Edwards Lifesciences Corporation.

subjects, may be unblinded to the randomization assignment to set up the devices in the OR accordingly. However, the delegated coordinator/designee must not reveal the randomization assignment to clinician prior to start of the surgery.

A baseline Creatinine, NT pro-BNP and Troponin will be drawn on the day of procedure. Any fluids and vasoactive medications administered, intraoperative complications, and adverse events that occurred during the procedure will be collected.

After surgery on post-operation day 1 (or within 24 hours of extubation), any fluids and vasoactive medications, post-operative complications, and adverse events will be collected. Troponin will be drawn and an MMSE will be administered.

[figure not shown]
Before hospital discharge (generally post-operation day 2-7, but may vary), another MMSE will be administered. Troponin and NT pro-BNP will be drawn POD1, 2, 3. Creatinine will be drawn POD 1, 2, 3.

While the subject is in the ICU, an ICU-specific Confusion Assessment Method (CAM-ICU 7) will be administered twice daily. This assessment will be administered for up to 7 days post-operation in the ICU or until the subject is transferred to the hospital floor.

While the subject is located on the hospital floor, a Brief Confusion Assessment Method (bCAM) be administered twice daily. This assessment will be administered until post-operation day 7 or until hospital discharge (whichever comes first).

Additional information will be collected when the subject is discharged. A 30-day follow up will take place 30 days (± 15 days) post-operation, either by phone call or in-person. If the follow-up takes place in-person, an MMSE will be administered at that time.

Figure 4. Sample Timeline Diagram

THIS DOCUMENT CONTAINS CONFIDENTIAL AND PROPRIETARY INFORMATION OF EDWARDS LIFESCIENCES, LLC. IT MAY NOT BE REPRODUCED OR DISCLOSED WITHOUT PRIOR WRITTEN PERMISSION FROM EDWARDS LIFESCIENCES, LLC.
 Edwards Lifesciences, Edwards, the stylized E logo, HemoSphere, Acumen IQ, Swan Ganz and ForeSight Elite are trademarks of Edwards Lifesciences Corporation.

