6. SCHEDULE OF EVENTS & PROCEDURES

Schedule of Events

Study Procedure / Exam	Subject Screening	Procedure	Day 1 Post-Op	Day 2-7 Post-Op	Discharge	30-Day Follow Up (±15 Days)
Obtain Informed Consent	X					
Perform Inclusion / Exclusion Evaluation	X					
Obtain Medical History / Subject Demographics ¹	X					
MMSE	X		X	X ²		X ³
Assign Subject ID		X				
Randomize Subject		X				
Enter Subject Data into Monitor		X				
Vital Signs		X				
NT pro-BNP		X	x	X ⁴		
Troponin		X	X	X ⁴		
Creatinine		X	X	X ⁵		
ABG Labs		X				
Basic Labs		X				
Monitoring Duration		X				
Data download from Monitor		X				
Obtain Fluid and Vasoactive Medication Administration Record ⁶		X	X			
CAM			X ⁷	X ⁸		
Complete eCRFs	X	X	X	X	X	X

¹ Medical History / Subject Demographics / Surgical and Clinician Demographics can be obtained prior to procedure, either at the screening visit or on the day of procedure.

² MMSE will likely take place between Day 2-7 Post-Op, but this may vary.

³ Only required for patients who will be returning to Wake Forest Baptist Medical Center for 30-day follow up

⁴ Troponin and NT Pro-BNP to be drawn on POD 1, 2 and 3

⁵ Creatinine to be collected on POD 1, 2 and 3

⁶ Can be collected via the hospital record system anytime on the day of procedure or thereafter.

⁷ CAM will be administered twice during post-op Day 1. While in the ICU, CAM-ICU 7 will be utilized. Once the subject is transferred to the hospital floor, bCAM will be utilized.

⁸ CAM will be administered twice per day until Day 7 Post-Op or until the subject is discharged (whichever occurs first). While in the ICU, CAM-ICU 7 will be utilized. Once the subject is transferred to the hospital floor, bCAM will be utilized.

THIS DOCUMENT CONTAINS CONFIDENTIAL AND PROPRIETARY INFORMATION OF EDWARDS LIFESCIENCES, LLC. IT MAY NOT BE REPRODUCED OR DISCLOSED WITHOUT PRIOR WRITTEN PERMISSION FROM EDWARDS LIFESCIENCES, LLC.

Edwards Lifesciences, Edwards, the stylized E logo, HemoSphere, Acumen IQ, Swan Ganz and ForeSight Elite are trademarks of Edwards Lifesciences Corporation.

HPI CARE Trial
Protocol #: 2020-19

Record Adverse Events, if applicable		X	X	X	X	X
30-day follow up / Mortality Determination						X

Procedure

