3.3. Secondary Endpoints

The following secondary endpoints will be analyzed:

- Additional definitions of hypotension:
 - Time Weighted Average (TWA) of MAP < 65 mmHg in the OR Period (T1)
 - TWA of MAP<65 mmHg in the CVICU Period (T2)
 - TWA of MAP < 65 mmHg in the CVICU Period, pre extubation (T3)
 - TWA of MAP < 65 mmHg in the CVICU Period, post extubation (T4)
 - Mean duration in minutes of MAP < 65 mmHg in the time periods of T1, T2, T3 and T4
 - Mean duration in minutes of MAP < 60 mmHg in the time periods of T1, T2, T3 and T4
 - Mean duration in minutes of MAP < 55 mmHg in the time periods of T1, T2, T3 and T4
 - Mean duration in minutes of MAP < 50 mmHg in the time periods of T1, T2, T3 and T4
- Clinical endpoints:
 - Acute kidney injury (AKI)⁷, as defined by the modified KDIGO criteria, stages 1, 2 and 3
 - Neurocognitive deficit, as evaluated by the MMSE, CAM-ICU⁷, and bCAM assessments. [bCAM will be used for delirium screening for patients who are deemed ready for transfer to the floor per ICU attending team's assessment, even if they are physically in the ICU]
 - Periprocedural Myocardial injury, measured with high-sensitivity Troponin I and defined by a threshold of 70 times the upper reference limit⁶. or >1400 pg/ml

 Edwards	Revision Date: May 7, 2024	Rev	For Use Only by Affiliates of Edwards Lifesciences	Page 10
	Title	A randomized trial of the Hypotension Prediction Index in the cardiac operating room and the intensive care unit		

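### The SAP states no use of the pre-operative MMSE in the neurocognitive endpoint, so precision is lost and pre-existing impairment can be counted as deficit

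*Combined protocol and SAP*

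**What the plan says.** **Measurement.** Protocol section 4 (Schema) has the MMSE given once the subject has consented, and the schedule of events in section 6 places it in the screening column. On post-operative day 1, or within 24 hours of extubation, "Troponin will be drawn and an MMSE will be administered". A further MMSE comes before discharge: "MMSE will likely take place between Day 2-7 Post-Op, but this may vary". At 30 days it depends on attendance: "If the follow-up takes place in-person, an MMSE will be administered at that time". The delirium tools are scheduled only after surgery; the first entry reads "CAM will be administered twice during post-op Day 1".

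**Endpoint.** Protocol sections 3 and 7 and SAP 3.3 and 8.4.2 all name the instruments and stop there: "Neurocognitive deficit, as evaluated by the MMSE, CAM-ICU 7, and bCAM assessments". None gives an MMSE cut-off, a required fall, a time point or a rule for combining the three tools.

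**Analysis.** SAP 8.4.2 uses the mITT population and closes with one sentence for all three clinical endpoints: "For each of the clinical endpoints, the rate in each arm and the difference in the rates for the arms will be presented". SAP 8.3 adds that secondary endpoints will be tested one-sided, at the level of the primary endpoint, if the primary succeeds.

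**Related design features.** No eligibility criterion concerns cognition. SAP 2.3 describes blocked randomization and names no stratification factor. The baseline comparison it promises applies only if assignments are skipped, and MMSE is not named there.

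**The concern.** A baseline measurement of the outcome is usually the most useful covariate available, and here the trial already schedules it. The planned analysis reduces a numeric score to yes or no and compares arms without that covariate. Both steps discard information.

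The second issue is what gets counted. Subjects with a low MMSE before surgery can enter. If deficit were read as a low post-operative score, such a subject with an unchanged score would count as an event, although guidance given after bypass could neither cause nor prevent it. Events of that kind occur at about the same frequency in both arms and pull the arm difference towards zero.

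At stake is how informative one of the three secondary clinical endpoints can be, and whether its definition is fixed before results are seen. The primary endpoint is not affected.

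**Working it through.** There is no figure in the plan to reproduce: neither document gives a rate, standard deviation, correlation or power for this endpoint. The first step is textual; the rest are illustrations on assumed inputs.

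**1. Is a reference to baseline written anywhere?** The three clinical endpoints in SAP 8.4.2 compare as follows.

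| Endpoint | Criterion given |
|---|---|
| Acute kidney injury | Modified KDIGO, by stage |
| Myocardial injury | Troponin threshold |
| Neurocognitive deficit | Instruments only |

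Elsewhere the SAP does write the reference in. SAP 8.6 sets CO/CI against a pre-induction baseline, sets cerebral desaturation against a baseline NIRS value, and counts only new-onset atrial fibrillation. Nothing comparable appears for the MMSE.

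**2. Precision of the score.** Assume equal variances before and after surgery and a correlation r between the two scores. Relative to an unadjusted comparison of post-operative scores, ANCOVA has variance ratio 1 − r², and a simple change score has 2(1 − r).

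| r (assumed) | ANCOVA ratio | Variance cut | SE cut | Change-score ratio |
|---|---|---|---|---|
| 0.3 | 1 − 0.09 = 0.91 | 9% | 5% | 1.4 |
| 0.5 | 1 − 0.25 = 0.75 | 25% | 13% | 1.0 |
| 0.7 | 1 − 0.49 = 0.51 | 49% | 29% | 0.6 |

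In terms of subjects, at r = 0.5 the planned 175 per arm would carry the information of 175 / 0.75 = 233 per arm analysed without adjustment. The change-score column shows why ANCOVA is preferred: at low correlation a plain change is worse than ignoring baseline. These ratios compare adjusted with unadjusted *scores*. The further loss from splitting the score into yes/no is not quantified here.

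**3. Dilution, if already-impaired subjects are counted.** Let a share q in both arms be impaired before surgery and always counted, and let p be the rate of new deficit in the rest. The observed rate is q + (1 − q)p, so the observed difference is (1 − q)(p₀ − p₁). Assume p₀ = 20% and p₁ = 0.7 × 20% = 14%, borrowing the 30% reduction planned for hypotension.

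| q (assumed) | Observed rates | Difference (points) | Rate ratio |
|---|---|---|---|
| 0% | 20.0% vs 14.0% | 6.0 | 0.70 |
| 5% | 24.0% vs 18.3% | 5.7 | 0.76 |
| 10% | 28.0% vs 22.6% | 5.4 | 0.81 |
| 20% | 36.0% vs 31.2% | 4.8 | 0.87 |

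Power at one-sided 0.025 with 157 per arm (the SAP 2.4.3 figure) falls from 29% to 23%, 20% and 14%. With a larger assumed effect, 20% vs 10%, and the final 175 per arm at two-sided 0.05, it is 75%, 51% and 36% at q = 0, 10% and 20%.

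**4. How much overlap could there be?** Take an assumed cut-off of below 24, pre-operative mean 26 to 28 with SD 2.2, post-operative SD 2.4, a mean fall of 1 point and r from 0.4 to 0.8. In a simulation on those inputs, 8% to 40% of subjects below the cut-off after surgery were already below it before. Under a definition based on decline, those subjects would not count merely for having started low.

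**The case against.** The strongest objection is that the documents never define deficit, so a reader may not infer that pre-existing impairment *is* counted. The word, together with a scheduled pre-operative MMSE, readily allows a fall from baseline, and under that reading the dilution in steps 3 and 4 does not arise. The sentence in SAP 8.4.2 is generic: it is equally silent on the baseline creatinine, yet nobody would conclude that kidney injury is judged without it. This stands. The text shows an omission, not a decision to ignore baseline. It does not remove the need to act: kidney injury has a named criterion and the MMSE has none, and a rate based on decline is still dichotomised and unadjusted.

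A reader might also infer that the arms are biased. That is not supported. Randomization balances prior impairment in expectation, and chance imbalance is ordinary sampling error covered by a valid interval.

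Three further points stand as limits. The power figures rest wholly on assumed rates and prevalence, and the trial was not sized on this endpoint. They also model the MMSE alone, while the listed endpoint includes two delirium tools with no scheduled pre-operative value, so dilution of a combined endpoint is unknown. Finally, the documents schedule the MMSE but do not show that it was captured; SAP section 10 records that SOFA, also a protocol item, never reached the EDC.

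**Conclusion.** The point holds in a limited form. The pre-operative MMSE is scheduled for every consented subject, the planned analysis is an unadjusted difference in rates, and no use of the baseline score is stated. The loss of precision follows however deficit is defined. Its size depends on a correlation the plan does not give: 9% to 49% of the variance of the score over an assumed range of 0.3 to 0.7.

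Dilution is possible but not shown. It needs a definition based on post-operative status alone, which the text neither states nor rules out. The stronger reading, that pre-existing impairment does count as deficit or that it favours one arm, goes beyond the documents. The expected consequence is dilution and lost precision, not bias. As this is a secondary endpoint with no stated power, the change is worth making but does not threaten the trial's main conclusion.

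**What to change.** In SAP 8.4.2, before results are seen:

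- Keep the rate per arm and the difference in rates, but define MMSE deficit as a pre-specified fall from the subject's own pre-operative MMSE, at named time points (day 1 and pre-discharge).
- Add an ANCOVA, or a mixed model across the two post-operative time points, for the MMSE score with baseline MMSE and arm. Report the adjusted mean difference with its 95% CI.
- Report delirium from CAM-ICU 7 and bCAM separately, since no change from baseline can be formed for those tools.
- State a rule for subjects without a post-operative MMSE, for example those still intubated or deceased. SAP 6.2 provides no imputation for them.

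No new assessments are needed, provided the scheduled MMSE scores are confirmed to be in the database. The cost is a little more analysis work, a check for ceiling effects (a rank-based ANCOVA would serve) and the missing-score rule. The adjusted mean difference answers a somewhat different question from the rate, so it should be added alongside the rate and not replace it.

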8.5. Subgroup Analyses

Subgroup analyses will be performed for the primary effectiveness, the primary safety, and the secondary endpoints. For each subgroup, the appropriate summary statistics will be presented for each arm individually and for the difference between the two arms. Where appropriate, a 95% confidence interval for the difference may also be presented. Subgroups will include but not limited to:

- Subgroup age stratification
- Subgroup gender
- Subgroup race (white versus non-white)

These subgroup analyses are not powered and no formal hypothesis testing will be performed.

8.6. Exploratory Analyses

The following exploratory analyses will be performed. These analyses will be presented for the FAS population.

- Protocol adherence to HPI alert, as defined by >50% HPI alerts with documented intervention per the suggested treatment algorithm within a 5-minute timeframe

 Edwards	Revision Date: May 7, 2024	Rev	For Use Only by Affiliates of Edwards Lifesciences	Page 18
	Title	A randomized trial of the Hypotension Prediction Index in the cardiac operating room and the intensive care unit		

For each subject, it is likely that there will be several decisions necessary. Each decision will be made separately, and the overall rate of compliance will be calculated.

A full definition of the compliance algorithm, can be found in section 12.2.

- Difference in time spent in hypertension defined as TWA of MAP>110, >120 and >130 mmHg post-cardiopulmonary bypass CPB) through the first 8-hour ICU period as compared with the control group. The time spent in hypertension will be calculated in a similar manner to the primary endpoint. The only difference will be that we are looking for the amount of time above the hypertension thresholds instead of below it. The average time will be calculated by arm and the difference will also be presented.
- In-hospital mortality rate
The mortality rate will be calculated as a simple proportion for each arm and for the difference between the two arms.
 - Incidence of cerebral desaturations defined as total time below 10% relative to baseline NIRS values. For each subject, the baseline NIRS value will be established at The time below 10%
- Percent of monitoring time with CO or CI within 10% relative to pre-induction baseline
The baseline CO and CI will be calculated pre-induction. The percent of the monitoring time within 10% of the baseline value will be calculated and presented by and for the difference between the arms.
- Hospital Length of Stay (days)
The hospital length of stay will be calculated starting with the procedure time until the subject is discharged. LoS will be calculated and presented by and for the difference between the arms.
- ICU Length of Stay (hours)
- Time to extubation (hours)
The time to extubation will be calculated as the amount of time from intubation until extubation. The average time will be presented by arm and the difference will also be presented.
- New onset atrial fibrillation, detected prior to ICU discharge
The proportion of patients with new onset afib will be presented by arm and the difference between the two arms.

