The Modified intent-to-treat (mITT) population is composed of all subjects who pass the screen (inclusion/exclusion) evaluation, sign the informed consent form (ICF), are assigned a subject ID, and are randomized to a study group. This includes roll-in and pivotal subjects.

B. FAS population

FAS (full analysis set) population is composed of all pivotal subjects with valid HemoSphere observations.

C. PP population

The per protocol (PP) population is composed of all pivotal subjects without protocol deviations.

D. CC population

The complete cases (CC) population is composed of all the pivotal subjects who complete surgery and complete the trial.

Analysis Methods for the Primary Endpoint

The primary study objective is to evaluate if the use of HPI software in conjunction with a treatment protocol can statistically reduce the study patient's hypotension duration by the measurements taken in the cardiac OR and ICU, which has been shown to correlate with morbidity and mortality. By the hypotheses designed in sample size calculation, the following t statistics will be used to judge if the hypotension duration of the study arm with HPI software is statistically shorter or smaller than the control arm without HPI software.

$$t = \frac{\widehat{\mu}_1 - \widehat{\mu}_0}{\sqrt{S_p^2 \left(\frac{1}{n_1} + \frac{1}{n_0} \right)}}$$

Here $\widehat{\mu}_1, \widehat{\mu}_0$ is the mean hypotension duration estimation of the test arm and reference arm, respectively. The pooled variance, $S_p^2 = \frac{(n_1-1)*S_1^2 + (n_0-1)*S_0^2}{n_1+n_0-2}$, n_1, n_0 is the final valid subjects in test arm and reference arms respectively, S_1^2 and S_0^2 are the variance estimates of the test arm and reference arm respectively.

By the t statistics calculated with the data from clinical operation, compares to the critical t value ($t(\alpha', n_1 + n_2 - 2)$) to judge if null hypothesis is rejected. Here α' is the split type I error by study design for interim analysis and the final analysis, $n_1 + n_2 - 2$ is the degree of freedom.

For the interim analysis, by Pocock methodology with one-sided t test, $\alpha' = 0.015$. If p value deduces from the actual t value with $n_1 + n_2 - 2$ degrees of freedom is less than α' , H_0 will be rejected.

For the final analysis, using the Pocock methodology, with one-sided t test, $\alpha' = 0.015$. A similar computation will be done at the interim analysis.

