1. INTRODUCTION

This statistical analysis plan (SAP) specifies the statistical methods to be implemented for the analysis of data collected within the scope of Edwards Lifesciences's Protocol, 2020-19 (version F), A randomized trial of the Hypotension Prediction Index in the cardiac operating room and the intensive care unit, provides detailed instructions to study data analysis. If there are conflictions between SAP and other study documents related to data analysis, SAP will be the final document that we will follow.

The primary analyses will be done using SAS, Version 9.4 or later version installed in Edwards Lifesciences' Server. The computation of hypotension duration for each hypotension instance, subject's total hypotension duration, and all other relevant endpoints will be completed with global macro function written with SAS, which is developed and maintained by department of critical care, Edwards Lifesciences.

R will be the support software used in a few applications, such as draw publication quality plots, and application of advanced statistical models in the analysis.

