4.2. Full Analysis Set (FAS) Population

The FAS population is a subset of the mITT population and will consist of all enrolled pivotal subjects who undergo cardiac surgery ≥ 2 hours duration with the aid of cardiopulmonary bypass, have one postoperative assessment, and have valid hemodynamic observations.

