9.1. Deaths

All deaths that occur for subjects during the study will be presented as the incidence rate and the relationship with the study device and the procedure. Deaths will be summarized for the mITT population by arm.

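### The exploratory in-hospital mortality rate (SAP 8.6) is computed on the FAS, which needs a postoperative assessment, so any death before that assessment drops out of the rate and the arm difference

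*Combined protocol and SAP*

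**What the plan says.** SAP 8.6 opens its list of exploratory analyses with one rule on the analysis set: "These analyses will be presented for the FAS population". In-hospital mortality is on that list, and no exception is made for it. Its method is given as: "The mortality rate will be calculated as a simple proportion for each arm and for the difference between the two arms".

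SAP 4.2 makes the FAS a subset of the mITT. Subjects must be enrolled pivotal subjects who "undergo cardiac surgery ≥ 2 hours duration with the aid of cardiopulmonary bypass", and who "have one postoperative assessment, and have valid hemodynamic observations". All of these conditions must be met. The SAP does not say what counts as the postoperative assessment or when it takes place.

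The protocol's definition (section 7, Analysis Populations) is wider: "FAS (full analysis set) population is composed of all pivotal subjects with valid HemoSphere observations". It asks for no postoperative assessment. SAP 1 settles which text applies: "If there are conflictions between SAP and other study documents related to data analysis, SAP will be the final document that we will follow". SAP 10, which lists departures from the protocol's analysis, mentions only the SOFA score.

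Elsewhere the SAP puts patient outcomes on the mITT. SAP 8.4.2 does so for the clinical secondary endpoints, SAP 8.2 and 9.2 for serious adverse events, and SAP 9.1 for deaths: "Deaths will be summarized for the mITT population by arm".

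**The concern.** Membership of the FAS is settled after randomisation and, through the assessment condition, depends on survival. For most endpoints in SAP 8.6 that is a question of data availability. For mortality it means that the outcome being counted helps decide who is counted: a patient must live to a postoperative assessment before a later death can enter the rate.

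At stake is the only comparison of in-hospital mortality between arms that the SAP plans. The protocol's Background cites earlier work linking intraoperative hypotension with in-hospital mortality, and the HPI-guided period starts after bypass in the operating room. A mortality rate that cannot include operating-room deaths leaves out part of the period in which the intervention acts.

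**Working it through.** No figure in the plan has to be reproduced here. The check sets the definitions side by side and then gives a sense of scale.

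**Step 1: which deaths leave the rate.**

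| FAS condition (SAP 4.2) | Does it remove an operating-room death? |
|---|---|
| Bypass surgery of at least 2 hours | Only if the operation ends before 2 hours |
| One postoperative assessment | Always, because none can have taken place |
| Valid hemodynamic observations | Rarely, because monitoring starts in the operating room (protocol 5; SAP 5.1) |

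The assessment condition does the work. It also removes a death after surgery but before the first assessment. How many deaths that covers cannot be determined, because the assessment is undefined.

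**Step 2: the same patient under the mITT.** SAP 4.1 requires passing screening, consent, a subject ID, randomisation, an arterial line and a connected sensor. None of these requires surviving surgery.

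**Step 3: size.** Inputs:
- N = 175 per arm (SAP 8.1.4), used for both sets apart from the early deaths.
- D in-hospital deaths per arm and e early deaths. Both are assumptions, since the documents give neither.

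Rate with all deaths: D/N. Rate with early deaths removed: (D − e)/(N − e).

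| D | all deaths | e = 1 | e = 2 | e = 3 |
|---|---|---|---|---|
| 3 | 3/175 = 1.71% | 2/174 = 1.15% | 1/173 = 0.58% | 0/172 = 0% |
| 5 | 5/175 = 2.86% | 4/174 = 2.30% | 3/173 = 1.73% | 2/172 = 1.16% |
| 7 | 7/175 = 4.00% | 6/174 = 3.45% | 5/173 = 2.89% | 4/172 = 2.33% |

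With e = 0 the two rates agree. Each early death lowers the rate by 0.55 to 0.58 percentage points, close to 1/175 = 0.57.

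**Step 4: arm difference, when early deaths fall in one arm only.**
- Five deaths in each arm, two early in arm A: the difference (A minus B) is 0 with all deaths, and 3/173 − 5/175 = 1.73% − 2.86%, about −1.1 points, on the FAS. The arm with the early deaths looks better.
- Six deaths in A and four in B, two early in A: the difference is 2/175 = +1.14 points with all deaths, and 4/173 − 4/175 = +0.03 on the FAS.
- The same totals with three early in A: 3/172 − 4/175 = −0.54 points, so the sign reverses.

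**The case against.** The strongest reply is that no mITT death disappears from the report. SAP 9.1 gives all deaths during the study as an incidence rate by arm on the mITT. Death is a serious adverse event by definition (SAP 9.2), so early deaths also enter the primary safety endpoint (SAP 8.2) and the event summaries, which show day 0 separately. The endpoint in 8.6 is exploratory, has no test specified for it and cannot change the trial's conclusion. This stands, and it limits the consequence. It does not remove the fault, because SAP 9.1 covers the whole study period to 30 days and plans no in-hospital arm difference.

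A second reply also stands in part. Some patients at high risk of dying in the operating room may be outside the mITT too. The exclusion criteria cover a return to bypass for instability and a post-pump LVEF below 15%, and SAP 4.6 counts included subjects who did not meet all the inclusion criteria as screen failures. Changing the analysis set would not recover deaths that are outside the mITT.

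Three stronger readings are tempting but are not supported:
- A reader might infer that the valid-data condition also removes operating-room deaths. Monitoring is already running by then, so it would seldom do so.
- A reader might infer that SAP 8.6 and 9.1 conflict because they give two mortality results. They count different things, in-hospital deaths and all deaths during the study, and could differ even on one shared set.
- A reader might infer that the reported rate is bound to be too low. It is too low only if a death occurs before the first assessment.

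**Conclusion.** The point holds for one exploratory endpoint. As written, SAP 8.6 with SAP 4.2 gives an in-hospital mortality rate conditional on surviving to an undefined postoperative assessment, and the arm difference inherits that condition. If early deaths occur, the rate is understated by roughly 0.6 percentage points per death at about 175 per arm. With five deaths per arm and two early deaths in one arm only, the difference shifts by about 1.1 points. These sizes rest on assumed counts of 3 to 7 deaths per arm with up to three of them early, and zero early deaths gives no effect. The primary effectiveness test and the mITT safety reporting are not affected by this point. It is worth correcting because the rule is biased in a known direction within an arm, departs from the SAP's own practice for clinical outcomes and deaths, and is simple to change.

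**What to change.** In SAP 8.6, state that in-hospital mortality and its arm difference are computed on the mITT population, pivotal subjects only, by randomised arm, with all such subjects in the denominator. This matches SAP 8.4.2 and 9.1. Pivotal subjects should be named because the protocol's mITT includes roll-in subjects, while SAP 4.5 analyses them separately. Keep the FAS for the monitor-derived exploratory measures, such as time in hypertension and time with CO or CI near baseline.

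The cost is one line of SAP text. The deaths are already collected and tabulated on the mITT, so no new data are needed.
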